Study Design:	
The study is an open-label pilot study in newly diagnosed GBM patients following surgery. Patients (≥ 22 years) with histologically confirmed GBM in the supratentorial region and a KPS $\geq 70\%$ are eligible to participate. Patients must have had MGMT testing performed locally for stratification purposes to participate, but specific MGMT result (positive, negative, or indeterminate) shall not be a cause for exclusion. Eligible patients will be receiving treatment with TTFields starting about 1 week prior to radiation. In addition to TTFields, they will receive radiation and temozolomide at a dose and schedule conforming to the standard of care. The expected toxicity is skin related and patients will be followed closely for weekly skin and neurological examination during the DLT window throughout radiation therapy and then for 8 weeks afterwards to capture any delayed toxicity as they begin adjuvant therapy per the standard of care. As long as tolerated and their conditions remain stable, patients shall continue the experimental therapy up to 24 months per the standard of care.
 
The study incorporates three stages of recruitment to confirm the safety of combining TTFields therapy with concurrent chemoradiation: a safety lead-in cohort of the first 6 patients enrolled, a second safety lead-in cohort of the first 15 patients enrolled (half of the total enrollment), and an expansion cohort with 15 additional patients. For the lead-in cohorts, a safety interim analysis will be performed 4 weeks after radiation of the

	last patient and will need to pass a pre-specified stopping rule before the next stage of recruitment can begin. Safety within the DLT window and efficacy analyses will be performed on all subjects at the end of the study. An exploratory analysis of radiation dosimetry will be performed by phantom modeling incorporating the TTFields electrode arrays prior to any patients being enrolled.

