Study Hypothesis:	TTFields has been shown to be safe and efficacious in large trials with glioblastoma patients in combination with adjuvant temozolomide but concurrent use together with trimodal therapy has not been examined in clinical trials. Our primary hypothesis is that the TTFields treatment, if initiated concurrently along with radiation and temozolomide therapy, would not significantly alter the safety profile. Secondarily, continuation of early initiated TTF along with adjuvant temozolomide treatment as per the standard of care would increase progression and overall survival. The primary hypothesis is safety and will be tested directly in this trial, but the secondary hypothesis would be assessed only with preliminary observations and need validation in a larger trial that is statistically powered for that investigation.
Sample Size:	30 patients total, 6 included in the first safety lead-in and 15 in the second safety lead-in.
Study Population:	Patients with newly diagnosed histologically confirmed glioblastoma after maximally safe resection, with MGMT methylation status in process, are eligible for enrollment.
Primary Endpoint:	The primary endpoint is safety and tolerability of the combined use of TTFields added to standard chemoradiation and TMZ.
Secondary Endpoints:	Our secondary endpoints will be progression-free and overall survival, imaging response by RANO criteria, and duration and compliance of TTF use.

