To form a reasonable basis of safety for enrolling the expansion cohort of patients, this study will incorporate two safety lead-ins using the first 6 patients and the first 15 patients (50% of the expected total number of patients) to assess the feasibility, safety and tolerability of combining TTFields therapy with concurrent chemoradiation (concurrent enrollment allowed). The safety cohorts will receive TTFields therapy in addition to standard of care. Variations in daily patient positioning will be recorded. Any treatment related adverse effects will be measured, assessed, and graded during the dose-limiting toxicities (DLT) period, from the beginning of therapy until 8 weeks after completion of radiation therapy to capture any potential delayed toxicity following combination (Trimodal) therapy with radiation, temozolomide, and TTFields therapy. DLT include any severe or life-threatening treatment-related adverse effects that preclude further administration of the study treatments, such as radiation, temozolomide, or continuation of TTFields therapy. The DLT assessment period will be limited to the time from start of TTFields through 8 weeks after RT's completion.

The first lead-in cohort will include the first 6 patients to finish the DLT period and be assessed by investigators. If a DLT occurs in 2 or more of the 6 patients, then the study will not move forward and may re-consider the goal dose of TTFields therapy in the main cohort to be reduced by 50% (one out of every two weeks off) and only increased to the standard usage of

continuous treatment 4 weeks after completion of radiation therapy. If a DLT occurs in less than two patients, the study will proceed with the second safety lead-in.

The second lead-in cohort will include the first 15 patients (6 from the first lead-in and 9 additional) to finish the DLT period and be assessed by the Data Safety Monitoring Committee (DSMC). If a DLT occurs in 5 or more of the 15 patients in the second safety cohort, then the study will not move forward with the expansion cohort and may re-consider the goal dose of TTFields therapy in the main cohort to be reduced by 50% (one out of every two weeks off) and only increased to the standard usage of continuous treatment 4 weeks after completion of radiation therapy. If a DLT occurs in less than five patients, the study will proceed with the final expansion cohort.

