- 4. Investigator judgment, safety** – Investigator may discontinue treatment due to concerns of safety. This includes significant neurological decline during treatment or requirement of steroids beyond the daily limit of 8mg of dexamethasone or bioequivalent dose for more than 7 consecutive days.
- 5. Lack of compliance** - The Sponsor or investigator may remove a patient from study therapy for lack of compliance to the study protocol. Patients who are using the TTField treatment less than 75% of the minimum recommended usage of 18 hours a day on average, as assessed monthly (13 hours a day or less), unless per officially instituted dose reduction, may be discontinued at the discretion of the investigator or sponsor.
- 6. Inter-current illness** – Illness that prevents further administration of treatment.

Enrollment Plan

a) Anticipated Start Date

- Dosimetric testing and analysis planned for September, 2019.
- Screening planned to begin November, 2019.

b) Total Expected Duration of the Clinical Trial

Anticipated duration of the trial will be 36 months from start of screening to completing two year long-term follow of the last patient enrolled.

c) Expected Duration of Each Subject's Participation

Up to 24 months from subject screening date to the point of study discontinuation based on specified criteria above or completion of the clinical trial.

e) Estimated Time Needed to Select the Required Number of Subjects (i.e., Enrollment Period)

The anticipated initial enrollment period for the 6 subjects in the lead-in cohort will be 4-8 weeks, with 3 subjects from each of the 2 study sites.

Following the interim analysis of safety for the lead-in cohort, there will be an expansion of enrollment to 15 patients, followed by another safety stop and interim analysis. The final cohort will comprise a total of 30 patients between the 2 participating sites. At least 1/3 of the subjects will be enrolled from each of the 2 study sites to ensure even enrollment (i.e., at least 10 subjects at each site). Anticipated duration for subject enrollment will be 6 to 12 months from start of screening to last subject enrolled in study.

Clinical Trial-Related Procedures

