In the event of a dose-limiting toxicity, the subject will be discontinued from treatment and followed for toxicity assessment and management and a joint decision will be made by the investigator and sponsor whether to adjust the dose or schedule for other subjects or permanently close the study for safety. In the event that more than 33% of subjects experience a DLT, the study cannot continue unless a modification is made to the level of the particular treatment to which that adverse event is definitely attributable. As preliminary safety stops, the study will include two safety lead-ins receiving TTFields with concurrent chemoradiation. These initial 6 and then 15 subjects will undergo interim analyses after completion of chemoradiation to determine if the expanded cohorts should be permitted enrollment as planned or if a dose reduction in TTFields of 50% of the scheduled use is warranted for safety.

Subjects will continue to receive study treatment until confirmed tumor progression, unacceptable toxicity, or other discontinuation criteria as described; subjects MUST discontinue investigational product (and non-investigational product at the discretion of the investigator) if they meet criteria for removal from study therapy as referenced in that section.

Toxicity related to TTFields treatment: Treatment-related adverse events (TRAEs) and severe treatment-related adverse events (STRAEs) will be assessed in the following ways.

- Patients will be evaluated by a neuro-oncologist or radiation oncologist for potential skin toxicity from TTFields therapy. Routine skin care recommendations will be provided, including use clobetasol cream prior to electrode placement and adjusting array placement to avoid continued site irritation. If there are concerns by investigator, the subject will be referred to a dermatologist for specialized evaluation. Neurological and general physical evaluations as well as laboratory assessments will also be conducted by a neuro-oncologist or radiation oncologist to identify other potential toxicities.
- In addition to clinic visits and interventions, Patients will also be supported by a technician from Novocure for device troubleshooting and compliance checks.
- All other adverse effects, either mild, or serious, will be triaged by a physician in coordination with the primary investigators of the study.

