Follow-up of Adverse Events

All adverse events will be followed with appropriate medical management until resolved. Patients discontinued from study therapy for unacceptable adverse events will be followed until resolution or stabilization of the adverse event and to the end of the study. For selected adverse events for which administration of the investigational device was stopped, a re-challenge of the subject with the investigational device may be conducted if considered both safe and ethical by the Investigator.

Adverse Events Monitoring

The Principal Investigator will review all adverse events and determine reportability to the DSMC and Providence's Institutional Review Board (IRB) per IRBAE reporting criteria; and, when the study is conducted under an Investigational Device Exemption (IDE), to the Food and Drug Administration (FDA) if it meets the FDA reporting criteria.

After the first 6 patients complete the lead-in phase, a written report will be submitted to the DSMC members describing the cohort, adverse events, and any Dose Limiting Toxicities observed, in accordance with the protocol. The report will be reviewed by the DSMC. Approval for the expansion cohort must be obtained from the DSMC prior to implementation.

Expedited Reporting

Reporting to the Data and Safety Monitoring Board

If a death occurs during the treatment phase of the study or within 30 days after the last administration of the study device and it is determined to be related either to the study device or to a study procedure, the Investigator or his/her designee must notify the PI, [name], or designee, Regulatory Manager, [name], within 1 business day of knowledge of the event. The contact may be by phone or e-mail. Death due to disease progression need not be reported to the PI or designee.

Reporting to Institutional Review Board

The Principal Investigator must report events meeting the IRB definition of "Unanticipated Problem" (UP) within 5 business days of his/her awareness of the event.

Expedited Reporting to the Food and Drug Administration

If the study is being conducted under an IDE, the Sponsor-Investigator is responsible for determining whether or not the suspected adverse reaction meets the criteria for expedited reporting in accordance with Federal Regulations (21 CFR §312.32).

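### The permission for concurrent enrollment is not limited to within a lead-in cohort; on one reading it undoes the recruitment holds after patients 6 and 15

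*Combined protocol and SAP*

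**What the plan says.** The stages are cumulative: "30 patients total, 6 included in the first safety lead-in and 15 in the second safety lead-in" (Section 1, Sample Size).

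Four places make later recruitment wait:

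- Section 1, Study Design: the interim analysis of each lead-in "will need to pass a pre-specified stopping rule before the next stage of recruitment can begin".
- Section 6, Enrollment Plan, item e: after the first analysis "there will be an expansion of enrollment to 15 patients, followed by another safety stop and interim analysis".
- Section 7, Dose Limiting Toxicity: the looks at 6 and 15 are there to "determine if the expanded cohorts should be permitted enrollment as planned".
- Section 7, Adverse Events Monitoring, after the report on the first 6 patients: "Approval for the expansion cohort must be obtained from the DSMC prior to implementation".

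Section 6, Safety Lead-ins, also makes progress depend on the DLT count (2 or more of 6, 5 or more of 15). The sentence that introduces both lead-ins, however, carries the unqualified parenthesis "concurrent enrollment allowed". The cohort is then defined by completion: "The first lead-in cohort will include the first 6 patients to finish the DLT period and be assessed by investigators". The second cohort is defined the same way but assessed by the DSMC. Section 1 instead describes the cohorts as the first 6 and the first 15 enrolled.

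On timing, item e says: "Anticipated duration for subject enrollment will be 6 to 12 months from start of screening to last subject enrolled in study". Item b gives 36 months for the whole trial, including two years of follow-up for the last patient.

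**The concern.** No sentence says that enrollment is suspended while patient 6 or patient 15 completes follow-up. A site could therefore cite Section 6 to keep enrolling. Defining the cohort by order of finishing leaves that reading open, because finishing order matters only if other patients are on study at the same time. If accrual did run on, the looks would come too late to limit how many patients receive a combination that, according to Section 4, no clinical trial had tested.

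The completion wording also affects the decision count. Taken literally, a patient who withdraws before the end of the DLT period never joins the cohort, and the next finisher takes that place in the 2-of-6 or 5-of-15 tally. If withdrawal is linked to toxicity, the count is biased towards continuing.

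**Working it through.** **Inputs**

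- Stage sizes: 6, 15 and 30 (Section 1).
- Lead-in pace: 6 patients in 4–8 weeks (Section 6, Enrollment Plan, item e), so r = 6/4 = 1.5 to 6/8 = 0.75 per week.
- Forecasts: accrual 6–12 months and trial 36 months (items e and b). The second equals 12 + 24.
- Look time D. The documents give three: 8 weeks after trimodal therapy, about Day 106 (Section 8 and the DLT period in Section 6); 4 weeks after radiation, about Day 78 (Section 1); after chemoradiation, about Day 49 (Section 7, Dose Limiting Toxicity).
- Assumptions: uniform accrual, total fixed at 30, lead-in pace persisting (no later-stage pace is given), no screening lag, no review time, 30.44 days per month.

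**1. The plan's own figure.** No derivation is given for 6–12 months. Without holds, 30/1.5 = 20 weeks (4.6 months) and 30/0.75 = 40 weeks (9.2 months). The stated range is therefore not the no-hold range.

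**2. Accrual with both holds.** T = 6/r + D + 9/r + D + 15/r = 30/r + 2D, with 30/r = 140 or 280 days.

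| Look time | Two holds alone | Fast pace | Slow pace |
|---|---|---|---|
| Day 106 | 212 d = 7.0 mo | 140 + 212 = 352 d = 11.6 mo | 280 + 212 = 492 d = 16.2 mo |
| Day 78 | 156 d = 5.1 mo | 296 d = 9.7 mo | 436 d = 14.3 mo |
| Day 49 | 98 d = 3.2 mo | 238 d = 7.8 mo | 378 d = 12.4 mo |

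Six months is not reached in any row. With Day-106 looks the two holds alone exceed it at any pace. Twelve months is reached in part of each range. For Day 106 it requires 6 patients every (365.25 − 212)/5 = 30.7 days, or 4.4 weeks, close to the fastest stated pace. Adding 24 months to the Day-106 range gives 35.6–40.2 months, against 36.

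**3. Enrollment at each decision if accrual did not pause.** N = min(30, k + rD), with k = 6 or 15 and D = 106 days.

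| Pace | First decision | Second decision |
|---|---|---|
| 30 in 6 months | 6 + 17.4 = 23.4 | 30 |
| 30 in 12 months | 6 + 8.7 = 14.7 | 23.7 |
| 6 in 4 weeks | 6 + 22.7 = 28.7 | 30 |
| 6 in 8 weeks | 6 + 11.4 = 17.4 | 26.4 |

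Over the same four paces, a Day-78 look gives 12.4–22.7 and 21.4–30. A Day-49 look gives 10.0–16.5 and 19.0–25.5. With the holds applied, the figures are 6 and 15 whatever the look time.

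**4. The count.** Section 1 ranks by enrollment and Section 6 by finishing. Section 6 (Early Termination Phone Visit) lets a subject who is unwilling to continue leave after a phone visit. Such a patient is in Section 1's first 6 but may not be in Section 6's. Section 7 (Evaluation of Safety) and Section 8 base analyses on patients with at least one day of device use, which matches neither definition.

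**The case against.** The strongest reply is that the holds are stated repeatedly and the parenthesis is three undefined words. It reads naturally as saying that patients within a lead-in need not be staggered, or that the two sites may enrol in parallel; item e plans 3 lead-in patients from each. This stands. A reader might infer that Section 6 flatly contradicts the holds, but the documents show only an ambiguity that conflicts on one of its readings.

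A reader might also infer that the forecast was built without holds. It was not shown to be. The no-hold time is 4.6–9.2 months, shorter than 6–12 at both ends, and 11.6 months with two full Day-106 holds lies inside the stated range. Shorter look times fit better still. Only the 6-month end fails.

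There are other safeguards. Under Section 7, a DLT leads to a joint decision on adjusting treatment or closing the study, the study cannot continue unmodified above 33% DLTs, and the DSMC reviews all SAEs. These reduce the risk but do not replace a look made before further patients enrol.

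On the count, finishing the DLT period is not the same as finishing treatment. Section 7 follows patients with a DLT and those discontinued for adverse events, and Section 6 allows continued observation. The problem is therefore confined to patients who leave follow-up.

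**Conclusion.** The point holds as an unresolved ambiguity with a material consequence on one reading. If enrollment ran on to Day-106 looks, about 15–23 of 30 (forecast pace) or 17–29 (lead-in pace, assumed to persist) would be enrolled before the first decision, and 24–30 before the second. These figures are conditional. It would be tempting to say that most of the 30 will be exposed before the looks, but the documents do not support that: with the holds as written it is 6 and then 15, and even without them about half at the 12-month pace.

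Separately, the 6-month end of the accrual forecast is not attainable with holds at the stated lead-in pace under any of the three look times, and the 12-month end is attainable only in part of each range. Review time and radiation running up to 7 days past Day 49 would lengthen these times. The cohort definition needs repair however the parenthesis was meant.

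**What to change.** 1. In Section 6, state that concurrent enrollment applies within a lead-in cohort only, and that enrollment pauses after patients 6 and 15 until the preceding look is passed.
2. Define the cohorts, in Sections 1 and 6 alike, as the first 6 and first 15 patients to start TTFields, counting those who stop early.
3. Reconcile the look time across Section 1, Section 7 (Dose Limiting Toxicity), and Sections 6 and 8.
4. Reconcile who decides the first look: investigators in Section 6, the DSMC in Section 7 (Adverse Events Monitoring).
5. Restate the accrual and 36-month forecasts for the look time chosen. If that is Day 106, they become about 12–16 and 36–40 months.

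The cost is a wording amendment and a longer stated timeline. The pauses are already required elsewhere in the protocol.
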